3.3. Primary Estimands

The primary estimands are defined as follows:

Treatment Comparison: depemokimab 100 mg SC + SoC compared to placebo + SoC

Population: Participants with a diagnosis of CRSwNP / ECRS

Co-primary variables/endpoints:

- Change from baseline in total endoscopic NP score at Week 52 (centrally read)
- Change from baseline in mean nasal obstruction score (verbal response scale [VRS]) from Week 49 through to Week 52

Summary measure: Difference in means between treatment groups - depemokimab 100 mg SC + SoC versus placebo + SoC

Main Intercurrent events (ICE) anticipated:

- Surgery, which includes any procedure involving instruments resulting in incision and removal of tissue from the nasal cavity (e.g., polypectomy and endoscopic sinus surgery (ESS)) to be handled using a composite strategy by incorporating occurrence of the event into the definition of the endpoint. Specifically, participants who undergo surgery will be assigned the worst possible value of the relevant score for all assessments following surgery (i.e., the worst value that it is possible to select on the given scale).
- Premature discontinuation of study treatment to be handled using a treatment policy strategy
- Initiation of a medication that may modulate the disease course of CRSwNP by reduction of blood eosinophils or type II inflammation to be handled using a composite strategy by incorporating the occurrence of the event into the definition of the endpoint. Medications that may modulate the disease course to be selected either based on published evidence or mechanism of action, and to include the initiation of some biologics, chronic SCS and INCS. Specifically, participants who start a medication that may modulate the disease course of CRSwNP will be assigned the

Protocol Amendment 5 Final

worst possible value of the relevant score for all assessments following the start of the medication (i.e., the worst value that is possible to select on the given scale).

- All other changes in background medication or start of a prohibited medication to be handled using a treatment policy strategy
- COVID-19 related events to be handled using a treatment policy strategy
- Course(s) of systemic CS for any reason to be handled using a treatment policy strategy

Supplementary estimand strategy for co-primary endpoints: In addition, the intercurrent event for all changes in background medication or start of medication that may modulate the disease course of CRSwNP to be handled under the treatment policy strategy will be considered as a supplementary estimand to the primary estimand.

3.4. Secondary Estimands

The secondary estimands are defined as follows:

Treatment Comparison: As for primary estimand

Population: As for primary estimand

Variables/endpoints:

- Change from baseline in mean symptom score for rhinorrhea (runny nose) (VRS) from Week 49 through to Week 52
- Change from baseline in mean symptom score for loss of smell (VRS) from Week 49 through to Week 52
- Change from baseline in Lund Mackay CT score at Week 52
- Change from baseline in SNOT-22 total score at Week 52
- Change from baseline in mean nasal obstruction score (VRS) from Week 21 through to Week 24
- Change from baseline in total endoscopic NP score at Week 26

Summary measure: As for primary estimand

Main Intercurrent events (ICE) anticipated: As for primary estimand

3.5. Secondary Estimands for Pre-specified Pooled Analysis Across Studies 218079 (This Study) and 217095

3.5.1. Secondary estimand for surgery endpoints

The secondary estimand for time to first nasal surgery (actual or entry on waiting list) or disease-modulating medication up to Week 52 and for time to first nasal surgery (actual) or disease-modulating medication up to Week 52 is defined as follows:

Protocol Amendment 5 Final

Treatment Comparison: depemokimab 100 mg SC + SoC compared to placebo + SoC

Population: participants with a diagnosis of CRSwNP / ECRS

Variable/endpoint:

- Time to first nasal surgery (actual or entry on waiting list) or disease-modulating medication for CRSwNP up to Week 52
- Time to first nasal surgery (actual) or disease-modulating medication for CRSwNP up to Week 52

Summary measure: Hazard ratio between treatment groups - depemokimab 100 mg SC + SoC versus placebo + SoC

Main Intercurrent events (ICE) anticipated:

- Premature discontinuation of study treatment to be handled using a treatment policy strategy
- Initiation of a medication that may modulate the disease course of CRSwNP by reduction of blood eosinophils or type II inflammation to be handled using a composite strategy by incorporating the occurrence of the event into the definition of the endpoint. Medications that may modulate the disease course to be selected either based on published evidence or mechanism of action, and to include the initiation of some biologics, chronic SCS and INCS. Specifically, participants who start a medication that may modulate the disease course of CRSwNP will be counted as requiring surgery at the time the medication was started.
 - All other changes in background medication or start of a prohibited medication to be handled using a treatment policy strategy
- COVID-19 related events to be handled using a treatment policy strategy
- Course(s) of systemic CS for any reason to be handled using a treatment policy strategy

Supplementary estimand strategy for pooled secondary endpoints related to nasal surgery:

- **Supplementary estimand 1:** In addition, the intercurrent event for all changes in background medication or start of medication (including those medications that may modulate the disease course of CRSwNP) to be handled under the treatment policy strategy will be considered as a supplementary estimand to the primary estimand.
- Supplementary estimand 2: In addition, the intercurrent event for initiation of a medication that may modulate the disease course of CRSwNP by reduction of blood eosinophils or type II inflammation to be handled under the hypothetical strategy. Medications that may modulate the disease course to be selected either based on published evidence or mechanism of action, and to include the initiation of some biologics, chronic SCS and INCS.
 - All other changes in background medication or start of a prohibited medication to be handled using a treatment policy strategy

3.5.2. Secondary estimand for systemic steroids endpoint

The secondary estimand for requiring at least 1 course of systemic corticosteroids or disease-modulating medication for CRSwNP or nasal surgery (actual) during the Week 52 treatment period is defined as follows:

Treatment Comparison: depemokimab 100 mg SC + SoC compared to placebo + SoC

Population: participants with a diagnosis of CRSwNP / ECRS

Variable/endpoint:

 Requiring at least 1 course of systemic corticosteroids or disease-modulating medication for CRSwNP or nasal surgery (actual) during the Week 52 treatment period

Summary measure: Odds ratio between treatment groups - depemokimab 100 mg SC + SoC versus placebo + SoC

Main Intercurrent events (ICE) anticipated:

- Surgery, which includes any procedure involving instruments resulting in incision and removal of tissue from the nasal cavity (e.g., polypectomy and ESS) to be handled using a composite strategy by incorporating occurrence of the event into the definition of the endpoint. Specifically, participants who undergo surgery will be counted as requiring systemic corticosteroids during the Week 52 treatment period.
- Premature discontinuation of study treatment to be handled using a treatment policy strategy
- Initiation of a medication that may modulate the disease course of CRSwNP by reduction of blood eosinophils or type II inflammation to be handled using a composite strategy by incorporating the occurrence of the event into the definition of the endpoint. Medications that may modulate the disease course to be selected either based on published evidence or mechanism of action, and to include the initiation of some biologics, chronic SCS and INCS. Specifically, participants who start a medication that may modulate the disease course of CRSwNP will be counted as requiring corticosteroids during the 52-week treatment period.
 - All other changes in background medication or start of a prohibited medication to be handled using a treatment policy strategy
- COVID-19 related events to be handled using a treatment policy strategy
- Course(s) of systemic CS for any reason to be handled using a treatment policy strategy

3.5.3. Secondary estimand for ACQ-5

The secondary estimand for change from baseline in ACQ-5 score at Week 52 is defined as follows:

Protocol Amendment 5 Final

Treatment Comparison: depemokimab 100 mg SC + SoC compared to placebo + SoC

Population: Participants with a diagnosis of CRSwNP / ECRS and partially or not wellcontrolled asthma with an ACQ-5 score >0.75 at baseline

Variable/endpoint:

Change from baseline in ACQ-5 score at Week 52

Summary measure: Difference in means between treatment groups - depemokimab 100 mg SC + SoC versus placebo + SoC

Main Intercurrent events (ICE) anticipated:

- Surgery, which includes any procedure involving instruments resulting in incision and removal of tissue from the nasal cavity (e.g., polypectomy and endoscopic sinus surgery (ESS)) – to be handled using a composite strategy by incorporating occurrence of the event into the definition of the endpoint. Specifically, participants who undergo surgery will be assigned a score of 6, the worst possible value of ACQ-5 for all assessments following surgery.
- Premature discontinuation of study treatment to be handled using a treatment policy strategy
- Initiation of a medication that may modulate the disease course of CRSwNP by reduction of blood eosinophils or type II inflammation to be handled using a composite strategy by incorporating the occurrence of the event into the definition of the endpoint. Medications that may modulate the disease course to be selected either based on published evidence or mechanism of action, and to include the initiation of some biologics, chronic SCS and INCS. Specifically, participants who start a medication that may modulate the disease course of CRSwNP will be assigned the worst possible value of the relevant score for all assessments following the start of the medication (i.e., the worst value that is possible to select on the given scale).
 - All other changes in background medication or start of a prohibited medication to be handled using a treatment policy strategy
- COVID-19 related events to be handled using a treatment policy strategy
- Course(s) of systemic CS for any reason to be handled using a treatment policy strategy

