To evaluate the pharmacokinetics and pharmacodynamics of depemokimab 100 mg SC + SoC in participants with a diagnosis of CRSwNP	Depemokimab plasma concentration at measured timepoints during the 52-week period			
	• Ratio to baseline in absolute blood eosinophil count at measured timepoints during the 52-week period.			

3.2. Objectives and Endpoints for Pre-specified Pooled Analysis Across Studies 218079 (This Study) and 217095 (Replicate Study)

Objectives	Endpoints			
Secondary: Pre-specified pooled analysis across studies 218079 (this study) and 217095 (replicate study)				
To evaluate the impact of depemokimab 100 mg SC + SoC compared to placebo + SoC on the requirement for nasal surgery (actual or planned) at Week 52 in patients with a diagnosis of CRSwNP To evaluate the impact on use of systemic corticosteroids of depemokimab 100 mg SC + SoC compared to placebo + SoC up to Week 52 in patients with a diagnosis of CRSwNP	 Time to first nasal surgery (actual or entry on waiting list) or disease-modulating medication for CRSwNP up to Week 52 Time to first nasal surgery (actual) or disease-modulating medication for CRSwNP up to Week 52 Requiring at least 1 course of systemic corticosteroids or disease-modulating medication for CRSwNP or nasal surgery (actual) during the Week 52 treatment period 			
To evaluate the impact on asthma control of depemokimab 100 mg SC + SoC compared to placebo + SoC at Week 52 in the sub-group of participants with partially or not well-controlled (ACQ-5 Score >0.75) asthma and a diagnosis of CRSwNP	Change from baseline in Asthma Control Questionnaire (ACQ-5) score at Week 52			

Objectives	Endpoints			
Other: Pre-specified pooled analysis across studies 218079 (this study) and 21709 (replicate study)				
To evaluate the impact of depemokimab 100 mg SC + SoC compared to placebo + SoC on nasal surgery and OCS use in patients with a diagnosis of CRSwNP	 Time to first nasal surgery (actual) or course of systemic CS or disease-modulating medication for CRSwNP up to Week 52 Time to first nasal surgery (actual or entry on waiting list) or course of systemic CS or disease-modulating medication for CRSwNP up to Week 52 			

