8.2.7.1. Asthma Control Questionnaire (ACQ-5)

The ACQ-5 is a 5-item questionnaire, which has been developed as a measure of patients' asthma control that can be quickly and easily completed [Juniper, 1999; Juniper, 2005]. The questions are designed to be self-completed by the participant. The 5 questions enquire about the frequency and/or severity of asthma symptoms over the previous week (nocturnal awakening on waking in the morning, activity limitation, and shortness of breath, wheeze). The response options for all these questions consist of a zero (no impairment/limitation) to six (total impairment/ limitation) scale. The recall period is the past week.

ACQ-5 will be assessed during the study according to Table 1.

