9.1.1. Multiplicity Adjustment

Hypotheses to be tested will be structured as shown in Figure 4. The co-primary endpoints will be tested first and if these comparisons are both significant at the two-sided 5% level, testing will continue within the study according to the testing procedure detailed in Figure 4. Testing of endpoints will be carried out in a hierarchical manner, dependent on statistical significance having been achieved for the previous endpoint in the hierarchy.

A pre-specified pooled analysis of data from this study (218079) and study 217095 is planned for the secondary endpoints of time to first nasal surgery (actual or entry on waiting list) or disease-modulating medication for CRSwNP, time to first nasal surgery (actual) or disease-modulating medication for CRSwNP, proportion of participants requiring at least 1 course of systemic corticosteroids or disease-modulating medication for CRSwNP or nasal surgery (actual), and ACQ-5 Score. This pooled analysis will be carried out after both studies have completed and only if statistical significance is achieved for both co-primary endpoints within both studies. Endpoints in the pooled analyses will be tested in a hierarchical manner at a significance level of α - α^2 (4.75%) [Bretz, 2019]. The time to first nasal surgery (actual) or disease-modulating medication for CRSwNP will only be tested if statistical significance is achieved for time to first nasal surgery (actual or entry on waiting list) or disease-modulating medication for CRSwNP. The proportion of participants requiring nasal surgery (actual) or at least 1 course of systemic corticosteroids or disease-modulating medication for CRSwNP will only be tested if statistical significance is achieved for both time to first nasal surgery

(actual or entry on waiting list) or disease-modulating medication for CRSwNP and time to first nasal surgery (actual) or disease-modulating medication for CRSwNP. Similarly, the ACQ-5 Score will only be tested if statistical significance is achieved for time to first nasal surgery (actual or entry on waiting list) or disease-modulating medication for CRSwNP, time to first nasal surgery (actual) or disease modulating medication for CRSwNP, and proportion of participants requiring at least 1 course of systemic corticosteroids or disease-modulating medication for CRSwNP or nasal surgery (actual).

Figure 4 Conceptualisation of Statistical Testing Strategy Across Studies 218079 and 217095

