The planned number of patients recruited within this study is not sufficient to adequately assess whether depemokimab significantly reduces the risk of nasal surgery compared to placebo. A pre-specified pooled analysis of data from this study (217095) and study 218079 is planned for the endpoint of time to first surgery (actual or entry on waiting list) or disease-modulating medication for CRSwNP. The proportion of participants in the pooled placebo group expected to require surgery or disease-modulating medication for CRSwNP is 23%. Assuming a true population hazard ratio of 0.38 (62% reduction in risk of required surgery) this pooled analysis has >90% power to observe statistical significance at the 2-sided 4.75% level. In the pooled analysis, the smallest observed effect which is predicted to result in a statistically significant difference between depemokimab 100 mg SC + SoC and placebo + SoC is a hazard ratio of 0.64 (36% reduction in risk of surgery).

The overall power for both co-primary endpoints and the pre-specified pooled analysis of time to first surgery (actual or entry on waiting list) or disease-modulating medication for CRSwNP using data from this study (217095) and study 218079 is >90%.

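### A significant pooled ACQ-5 result would not by itself show better asthma control, because nasal surgery or a CRSwNP drug start is scored as ACQ-5 = 6

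*Protocol*

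**What the plan says.** The ACQ-5 objective in Protocol Section 3.2 (and in the synopsis) reads "To evaluate the impact on asthma control of depemokimab 100 mg SC + SoC compared to placebo + SoC at Week 52", in participants with a baseline ACQ-5 above 0.75. Section 8.2.7.1 describes the instrument: "The 5 questions enquire about the frequency and/or severity of asthma symptoms over the previous week". On scoring it says "The response options for all these questions consist of a zero (no impairment/limitation) to six (total impairment/ limitation) scale".

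Section 3.5.3 defines the estimand as a difference in mean change at Week 52, with two composite rules. For surgery, "participants who undergo surgery will be assigned a score of 6, the worst possible value of ACQ-5 for all assessments following surgery". For medication, "participants who start a medication that may modulate the disease course of CRSwNP will be assigned the worst possible value of the relevant score", which on this scale is again 6. The medications named include some biologics, chronic systemic corticosteroids and INCS.

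ACQ-5 is the fourth and last test in the pooled hierarchy, at a two-sided 4.75% level. Section 9.1.1 says "the ACQ-5 Score will only be tested if statistical significance is achieved for time to first nasal surgery" in both its versions (with and without waiting-list entry, each combined with disease-modulating medication), and for the steroid, medication or surgery composite as well.

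The co-primary endpoints have a supplementary estimand in Section 3.3, under which medication changes are "to be handled under the treatment policy strategy will be considered as a supplementary estimand to the primary estimand". The pooled surgery endpoints have two in Section 3.5.1. Section 3.5.3 lists none. SAP Section 4.4.1 uses a milder composite for SF-36 and WPAI-GH: the participant's own worst score observed before the event. SAP Sections 1, 2.1 and 6.2.1 leave the ACQ-5 analysis to a pooled SAP that is not among the documents.

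**The concern.** For NP score or nasal obstruction, surgery is a failure of the disease being scored, so the worst value is a natural composite. For ACQ-5, nasal surgery is a failure in a different disease. The rule replaces whatever the participant reported about asthma with total impairment, at every later visit.

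The hypothesis tested is therefore about a mixture of asthma score and nasal event rate. If depemokimab reduces nasal surgery and drug starts but leaves asthma control unchanged, the arms still differ on this endpoint. The order of testing does not guard against that, because ACQ-5 is reached only once the nasal endpoints have separated. The ACQ-5 responder endpoint in Section 3.2 also counts a prior nasal event as failure, so it does not separate the two effects either. At stake is the wording of a multiplicity-controlled secondary claim.

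**Working it through.** **1. The plan's own figures.** Section 9.5 states: "The proportion of participants in the pooled placebo group expected to require surgery or disease-modulating medication for CRSwNP is 23" (per cent), with a hazard ratio of 0.38. The implied depemokimab rate is 1 − (1 − 0.23)^0.38 = 9.45%. The level is 0.05 − 0.05² = 0.0475, so z = 1.98. Assume that the replicate study is the same size, giving 250 per arm pooled.

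- Events = 250 × (0.23 + 0.0945) = 81.1.
- Critical hazard ratio = exp(−2 × 1.98/√81.1) = 0.644. With 236 evaluable per arm it is 0.636. The plan states 0.64.
- Power is 98.8–99.1% (Schoenfeld) or 97.4–98.1% (Freedman). The plan states above 90%.

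These reproduce. The documents give no power, mean, SD or subgroup size for ACQ-5.

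**2. Expected ACQ-5 difference with no asthma effect.** If the true Week 52 mean is m in both arms, assigning 6 after an event shifts the difference by −(pP − pD) × (6 − m), where pP and pD are the placebo and depemokimab event rates and pD = 1 − (1 − pP)^0.38.

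Waiting-list entry is part of the 23% but does not trigger a 6, so 23% is an upper anchor and lower rates are needed.

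**3. Chance of a significant result favouring drug.** Assumptions:

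- 50 to 100 participants per arm with baseline ACQ-5 above 0.75
- baseline mean 2.0 and SD 0.9
- the same 0.5-point improvement in both arms, with noise SD 1.0 and scores kept within 0 to 6; this gives m of about 1.61, so 6 − m is about 4.39
- ANCOVA at Week 52, adjusted for baseline, standing in for the planned MMRM
- two-sided 4.75% level

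| Placebo rate of actual surgery or drug start | Depemokimab rate | Expected difference | 50 per arm | 100 per arm |
|---|---|---|---|---|
| 5% | 1.93% | −0.0307 × 4.39 = −0.13 | about 7% | about 12% |
| 10% | 3.92% | −0.0608 × 4.39 = −0.27 | about 14% | about 25% |
| 15% | 5.99% | −0.0901 × 4.39 = −0.40 | about 21% | about 40% |
| 23% | 9.45% | −0.1355 × 4.39 = −0.59 | about 36% | about 62% |

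The nominal rate in that direction is about 2.4%. Repeat simulations move these entries by about one percentage point. Varying the Week 52 mean over 1.0 to 2.0 gives 35–40% (50 per arm) and 63–68% (100 per arm) at the 23% rate. Varying the SD over 0.7 to 1.3 gives 48–56% at 75 per arm and 23%.

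**4. Controls (75 per arm, 23% on placebo).**

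- Observed scores after the event: difference 0.00; 2.3% favour drug, 4.6% significant in either direction.
- Score of 6, equal event rates in the arms: 4.7% significant in either direction.
- Own worst pre-event score, as for SF-36 and WPAI-GH (with an assumed pre-event worst): difference about −0.12; 13% favour drug.
- Score of 6 as written, hazard ratio 0.38: difference about −0.60; 51–53% favour drug.

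So the effect comes from the assigned value combined with unequal event rates.

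**5. Does the test order help?** Requiring both surgery endpoints to be significant first, with 40–100% of the 23% being actual surgery or medication, the chance is 17–65% over 50 to 100 per arm (true Week 52 mean 1.5). The steroid composite was not included as a condition in that run.

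**The case against.** The composite is declared openly, and the protocol's summary of changes ties the medication rule to regulatory guidance. For that estimand the test keeps its level. A reader might call the percentages above a false-positive rate, but they are not one: they measure how often the declared composite separates when asthma control does not. This stands, and it confines the point to what a significant result may be said to show.

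There is also a case for a composite after medication. Some of the biologics concerned also treat asthma (Sections 1.1 and 5.2), so observed ACQ-5 after such a start mixes in other active therapy. INCS initiation is essentially confined to Japan, since INCS is mandatory elsewhere. This supports keeping the composite as the tested estimand if wanted. It does not remove the need to show the observed scores.

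Event rates in the ACQ-5 subgroup are unknown, and significance on the nasal endpoints in the whole pooled population does not prove an imbalance within that subgroup. This stands too, and is why a range is given. The pooled SAP may already contain an observed-score analysis. That cannot be checked, but Section 3.5.3 defines the estimand and lists none.

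Finally, the count of asthma exacerbations (Section 3.2) carries no nasal-surgery rule in its definition. It is an unadjusted other endpoint measuring something different, so it does not rescue the interpretation of ACQ-5.

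**Conclusion.** The point holds as one of interpretation. A significant pooled ACQ-5 difference cannot alone support a statement about asthma control. The spurious mean difference is about −0.13 to −0.6. Its size rests on the rate of actual surgery or drug start in the subgroup, on a hazard ratio of 0.38 applying there, and on the assumed ACQ-5 distribution and subgroup size.

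Three stronger readings are tempting and are not supported:

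- **That the test could be won with asthma control worse on drug.** If asthma is 0.3 points worse (100 per arm), the chance of a significant result favouring drug is 27% at a 23% placebo rate, but 8% at 15%, about 2% at 10% and 0.2% at 5%. At rates of 10% or below the claim fails.
- **That the rule destroys power for a real asthma benefit.** That calculation needs equal event rates in the arms, and the preceding nasal tests would then rarely succeed, so ACQ-5 would rarely be formally tested.
- **That the spurious difference exceeds the protocol's meaningful change of 0.5.** In Section 3.2 that threshold is a within-participant responder criterion, not a between-arm difference in means.

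**What to change.** Keep the composite as the tested estimand if preferred, and add the following to Section 3.5.3 and the pooled SAP:

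1. A supplementary ACQ-5 estimand that handles both nasal surgery and disease-modulating medication by treatment policy, using the scores reported after the event. Copying the Section 3.3 wording would not be enough, since it covers medication but not surgery. Removing only the surgery rule would leave the 6 for medication in place.
2. The same observed-score version of the ACQ-5 responder endpoint.
3. The number of participants with an assigned 6, by arm and by type of event.
4. A statement that the result will be described as an effect on asthma control only if the observed-score estimate agrees with the composite.

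The cost is wording, one extra model run and the matching responder output. No new data are needed: ACQ-5 is scheduled through Week 52, and Section 7.1 allows surgery without discontinuing study intervention. The drawback is that the observed-score estimate may be smaller if surgery or a started biologic improves asthma in placebo participants.
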